**13) Data and Specimen Banking**

*n/a.*

**14) Data Management and Confidentiality**

**STATISTICAL CONSIDERATIONS**

The primary objective of this study is to evaluate whether abatacept is effective in inducing a biochemical response in PBC patients with an incomplete response to UDCA.

The secondary objectives of this study are:

- To assess the safety of abatacept in patients with PBC
- To assess effect of abatacept on liver stiffness as a measure of liver fibrosis in patients with PBC
- To determine the effects of abatacept on immunologic markers of PBC
- To assess the impact of abatacept on the quality of life in patients with PBC
- To characterize pharmacokinetics (PK) of abatacept 125mg administrated SC weekly in patients with PBC
- To assess immunogenicity of abatacept 125mg administered SC weekly in patients with PBC

**Sample Size Determination**

Among patients with PBC who do not have a complete biochemical response to UDCA, the probability of achieving serum liver biochemical normalization spontaneously is <5%. If abatacept is found to be ineffective among 20 enrolled subjects, the probability of observing 3 or fewer treatment responses is >98%. If abatacept is associated with a treatment success response rate of 30% or more, then the probability of 4 or more individuals responding is 89%. If these endpoints were met, pursuit of a randomized, double-blind, placebo-controlled trial would then be justified.

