**5) Background**

**Introduction**

Primary biliary cirrhosis (PBC) is a progressive autoimmune disease of biliary epithelial cells resulting in biliary cirrhosis. The prevalence of PBC in the US and Europe is estimated to be 5-40 per 100,000 persons and accounts for 3-4 % of liver transplants performed in the US. The only approved medical therapy of PBC is the hydrophilic bile acid ursodeoxycholic acid (UDCA). Multiple studies suggest that UDCA delays progression of the disease, particularly those that have a biochemical response which has defined by multiple criteria, the simplest being a decrease of the alkaline phosphatase to 1.67 times the upper limit of normal. However, 20-40% of PBC patients have an incomplete response to UDCA and remain at significant risk of disease progression leading to death or liver transplantation.

PBC is characterized by a 90% female predominance, high titers of serum anti-mitochondrial autoantibodies (AMA) directed against the pyruvate dehydrogenase complex E2 subunit and elevated plasma levels of immunoglobulin M (IgM). However, evidence from both human and murine models suggests that T-cells, particularly CD8+ T cells, are key to the destruction of bile ducts. Genetic evidence of a T-cell defect is also supported by our findings and those of others demonstrating significant associations between CTLA-4 polymorphisms and PBC. Most notable, are the results we recently published in our murine model of PBC in which both AMA and biliary inflammation are induced by immunization with the xenobiotic 2-octynoic acid (2-OA). CTLA-4 Ig treatment one day before 2-OA immunization, completely inhibited AMA production, intra-hepatic T cell infiltrates, and bile duct damage. More critically, treatment with CTLA-4 Ig initiated after the 2-OA immunization and development of disease, also resulted in reduced intra-hepatic T cell infiltrates and biliary cell damage, although AMA levels were not altered.

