#### **2. Target Population**

- a) Confirmed PBC diagnosis based upon at least 2 of 3 criteria
  - i) AMA titer > 1:40
  - ii) Alkaline phosphatase > 1.5 times the upper limit of normal for at least 6 months
  - iii) Liver biopsy findings consistent with PBC

PROTOCOL TITLE: ABATACEPT FOR THE TREATMENT OF PRIMARY  
BILIARY CIRRHOSIS WITH AN INCOMPLETE BIOCHEMICAL RESPONSE TO  
URSODEOXYCHOLIC ACID

- b) Incomplete response to UDCA defined by an alkaline phosphatase  $> 1.67$  times the upper limit of normal after 6 months of UDCA at a minimum dose of 13 mg/kg/d.
- c) Taking a stable dose of UDCA for at least 3 months prior to Day 0.
- d) Willing and able to comply with all study requirements.
- e) AST and ALT  $\leq 5$  X the upper limit of normal

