## 11) Study Endpoints

The primary endpoint assessment will be the biochemical response rate defined by normalization of alkaline phosphatase or decrease of alkaline phosphatase by > 40% of the Day 0 level at 24 weeks of treatment.

Secondary endpoints will include:

- Absolute and percent change in alkaline phosphatase from Day 0 to 24 weeks.
- Absolute and percent change in alanine transferase (ALT) from Day 0 to 24 weeks.
- Change in liver stiffness from Day 0 to week 24 as measured by magnetic resonance elastography.
- Change in quality of life measured by change in PBC-40 from Day 0 to week 24.
- Change in AMA titer from Day 0 to week 24
- Change in IgM level from Day 0 to week 24
- Change in CD4+CD44+CD62L- and CD8+CD44+CD62L- frequencies in PBMC from Day 0 to week 24
- Comparisons of safety assessments pre-treatment, on-treatment, and post-treatment including adverse events, laboratory observations, and physical exam findings.
- Trough concentrations of abatacept concentrations from Week 0 to Week 24
- Immunogenicity evaluated over time by measuring anti-abatacept antibodies and anti-CTLA-4-T antibodies

PROTOCOL TITLE: ABATACEPT FOR THE TREATMENT OF PRIMARY BILIARY CIRRHOSIS WITH AN INCOMPLETE BIOCHEMICAL RESPONSE TO URSDODEOXYCHOLIC ACID

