### **Endpoint Definitions**

The primary endpoint assessment will be the biochemical response rate defined by normalization of alkaline phosphatase or decrease of alkaline phosphatase by > 40% of the Day 0 level at 24 weeks of treatment.

Secondary endpoints will include:

- Absolute and percent change in alkaline phosphatase from Day 0 to 24 weeks.
- Absolute and percent change in alanine transferase (ALT) from Day 0 to 24 weeks.
- Change in liver stiffness from Day 0 to week 24 as measured by magnetic resonance elastography.
- Change in quality of life measured by change in PBC-40 from Day 0 to week 24.
- Change in AMA titer from Day 0 to week 24
- Change in IgM level from Day 0 to week 24
- Change in CD4+CD44+CD62L- and CD8+CD44+CD62L- frequencies in PBMC from Day 0 to week 24
- Comparisons of safety assessments pre-treatment, on-treatment, and post-treatment including adverse events, laboratory observations, and physical exam findings.
- Trough concentrations of abatacept from week 0 to week 24
- Immunogenicity evaluated over time by measuring serum anti-abatacept antibodies and anti-CTLA-4-T antibodies

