### **Analyses**

Endpoints of efficacy will be compared between Day 0 and Week 24 using paired t-test (or Wilcoxon signed rank test as indicated) for continuous variables and Chi-square test

PROTOCOL TITLE: ABATACEPT FOR THE TREATMENT OF PRIMARY  
BILIARY CIRRHOSIS WITH AN INCOMPLETE BIOCHEMICAL RESPONSE TO  
URSODEOXYCHOLIC ACID

(or Fisher's exact test) for categorical variables. For variables measured at multiple time points, Repeated Measures ANOVA will be employed. All analyses will be two-tailed and P values less than 0.05 will be considered as statistically significant.

The primary endpoint assessment will be the biochemical response rate defined by normalization of alkaline phosphatase or decrease of alkaline phosphatase by > 40% of the Day 0 level at 24 weeks of treatment. We will report the observed biochemical response rate and a 95% confidence interval for the expected biochemical response rate.

We will assess each of the secondary endpoints: absolute and percent change in alkaline phosphatase, absolute and percent change in alanine transferase (ALT), change in liver stiffness as measured by magnetic resonance elastography, change in quality of life measured by change in PBC-40, change in AMA titer, change in IgM level, and change in CD4+CD44+CD62L- and CD8+CD44+CD62L- frequencies in PBMC from Day 0 to week 24 by paired t-test or Wilcoxon signed-rank test when appropriate. Because these endpoints will be generated with these studies, to solve the problem of the above multiple significance testing, we will use the false discovery rate proposed by Benjamini and Hochberg. In addition, PK and immunogenicity of abatacept in patients with PBC will be estimated.

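### The >98% protection claimed for the 4-of-20 rule comes from a rate of spontaneous normalization, not from a background rate for the composite response that the rule counts

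*Combined protocol and SAP*

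**What the plan says.** Section 14, Sample Size Determination, gives one background figure: "the probability of achieving serum liver biochemical normalization spontaneously is <5" percent. It does not say which liver tests must normalize or over what period.

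The next sentence applies a probability to a differently named event: "If abatacept is found to be ineffective among 20 enrolled subjects, the probability of observing 3 or fewer treatment responses is >98" percent. The paragraph adds an 89% chance of 4 or more responders at a response rate of 30%, and concludes: "If these endpoints were met, pursuit of a randomized, double-blind, placebo-controlled trial would then be justified".

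The response itself is defined elsewhere. Section 11 (Study Endpoints) and Endpoint Definitions in section 14 make the primary endpoint "normalization of alkaline phosphatase or decrease of alkaline phosphatase by > 40% of the Day 0 level at 24 weeks of treatment". Analyses repeats that definition and adds: "We will report the observed biochemical response rate and a 95% confidence interval for the expected biochemical response rate". It names no reference rate for the interval and no interval method.

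**The concern.** A single-arm go rule protects against a false go only as well as its null rate describes the event being counted. Here the null describes normalization, while the count includes anyone with a fall of more than 40%, normal or not. A null borrowed from a narrower event can be too low for a wider one, and the chance of 4 or more responders from background change alone would then be understated.

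What is at stake is how a bare go is read. Taken as written, the plan would credit 4 responders in 20 with a false-go chance below 2%, on a rate never given for that endpoint. The study is open label with no control group, and the 4-of-20 rule is what the plan offers as justification for a randomized trial.

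**Working it through.** **Inputs from the plan.** N = 20, go at 4 or more, null rate below 5% (5% used as the upper bound), alternative 30%: all from Sample Size Determination. Event counted: the primary endpoint in section 11 and Endpoint Definitions. One inference is needed: the paragraph does not define its treatment responses, but no other biochemical response endpoint is defined for the trial.

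**Step 1: reproduce the plan's figures.** With X ~ Binomial(20, p), P(X ≤ 3) = Σ C(20,k) p^k (1−p)^(20−k) for k = 0 to 3.

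- p = 0.05: 0.3585 + 0.3774 + 0.1887 + 0.0596 = 0.984 (0.9841 unrounded). This agrees with >98%. P(X ≥ 4) = 1 − 0.9841 = 0.0159.
- p = 0.30: P(X ≥ 4) = 0.8929. This agrees with 89%.

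The arithmetic is correct, and the >98% is what the 5% normalization rate yields.

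**Step 2: compare the two events.**

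- *At the same time point.* Everyone whose ALP normalizes is a responder, so P(composite) ≥ P(ALP normalization). If the benchmark requires other tests to normalize as well as ALP, it is narrower still.
- *The events can differ.* A fall of just over 40% from 3 × ULN ends just under 0.6 × 3 = 1.8 × ULN: a response, but not normal.
- *At the entry level.* Target Population requires ALP above 1.67 "times the upper limit of normal after 6 months of UDCA". A fall from 1.67 to 1.0 × ULN is 1 − 1/1.67 = 40.1%. For anyone still above 1.67 × ULN on Day 0, normalization is already a fall of more than 40%, so the endpoint reduces to the 40% criterion. The criterion does not explicitly fix the Day 0 value.
- *Different windows.* If the <5% refers to a period longer than 24 weeks, the week-24 rate could be lower. The direction of any error is therefore not settled until the window is stated.

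**Step 3: how the rule behaves at other background rates.** The documents give no background rate for the composite, so every rate in this table is an assumption.

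| Assumed composite background rate | P(3 or fewer of 20) | P(4 or more), false go |
|---|---|---|
| 3% | 99.7% | 0.3% |
| 4% | 99.3% | 0.7% |
| 5% | 98.4% | 1.6% |
| 6% | 97.1% | 2.9% |
| 7.5% | 94.2% | 5.8% |
| 10% | 86.7% | 13.3% |

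Solving for p, P(X ≤ 3) = 98% at p = 5.36%, and P(X ≥ 4) = 5% at p = 7.1%.

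The calculation assumes independent subjects with a common rate and all 20 counted.

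**The case against.** The strongest reply is that no error has been shown. The plan gives an upper bound, not a point value, and at 3% or 4% the protection is better than stated. Every unfavourable row in the table is an assumption. The word normalization may be loose shorthand for the composite, and the source behind the <5% may deal with exactly that endpoint. All of this stands, and it limits the point to a figure that is unsupported. It does not remove the point: as written, the paragraph names one event and the rule counts another. If the wording is shorthand, saying so and giving the basis settles the matter.

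It is also fair that the consequence is limited. A go leads only to a controlled trial, and the observed rate will be reported with a 95% confidence interval. That interval shows precision; the plan gives no composite background rate to set it against.

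Three stronger readings are tempting and are not supported:

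- *That the >98% is wrong, or that the true false-go risk is 6% or 13%.* Nothing in the documents puts the composite background rate at 7.5% or 10%.
- *That the rule fails once the background rate passes 5.36%.* The plan reports >98% but nowhere requires it. The false-go chance is still only 5% at about 7.1%.
- *That the Introduction adds a competing endpoint.* Its phrase "the simplest being a decrease of the alkaline phosphatase to 1.67 times the upper limit of normal" describes one of several published criteria for response to UDCA. It is background, not a definition for this trial.

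**Conclusion.** The concern holds as a mismatch between null and endpoint. The plan takes a rate below 5% for spontaneous normalization, with tests and time window unstated, and applies the resulting >98% to a composite that at the same time point is at least as frequent as ALP normalization. The figure is correct for a 5% null, but that null is not established for the response that the 4-of-20 rule counts.

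How much this matters depends on a rate the documents do not give: very little if the composite background rate is about 5% or lower, and more if it exceeds roughly 7%. The conclusion rests on reading treatment responses as the primary endpoint. Confidence is high that the wording does not match; there is no basis for claiming that the false-go risk is in fact understated. Severity is minor to moderate.

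**What to change.** In Sample Size Determination:

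1. State the event, the time window and the basis of the null for the week-24 composite, or label the rate an assumption.
2. Replace the single >98% with the operating characteristics of the existing rule. Suggested text: *Under assumed background response rates of 5%, 7.5% and 10%, the probability of 3 or fewer responses in 20 is 98.4%, 94.2% and 86.7%; the probability of 4 or more is 89% at a response rate of 30%.*

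In Analyses, add the week-24 ALP-normalization rate as a descriptive result. Compare it with the <5% benchmark only if that benchmark is confirmed to be for ALP normalization over a comparable window; otherwise one unverified match replaces another.

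The cost is one reworded paragraph, a basis for the null, and one extra rate from ALP values already collected. The stated protection may look less favourable. No patients or visits are added, and the sample size, the 4-of-20 threshold and the 89% are unchanged.

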**Populations for Analyses**

The primary analysis set for efficacy and safety analyses will include all subjects who received at least one dose of study drug.

**PROTOCOL TITLE: ABATACEPT FOR THE TREATMENT OF PRIMARY BILIARY CIRRHOSIS WITH AN INCOMPLETE BIOCHEMICAL RESPONSE TO URSODEOXYCHOLIC ACID**

**Pharmacokinetic Analysis Population:** All available plasma concentration data from subjects who receive at least 1 dose of study medication and have at least 1 concentration result will be reported. However, only subjects without dose interruption will be included in the summary statistics.

**Immunogenicity Analysis Population:** For immunogenicity samples, included all subjects who receive at least 1 dose of abatacept and have at least 1 immunogenicity result reported.

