## 12) Procedures Involved

This is an open label, active treatment trial to assess the efficacy and safety of abatacept in subject with PBC who have had an incomplete biochemical response to UDCA.

In this trial, 20 subjects with PBC who have had an incomplete biochemical response to UDCA will be assigned to treatment with weekly subcutaneous injections of 125 mg of abatacept.

The treatment phase of the study will last 24 weeks with an off-treatment follow up at Week 36.

All subjects will undergo blood chemistry panel, complete blood count, INR, AMA, magnetic resonance elastography (MRE), and PBC-40 survey prior to the first dose of study drug. Baseline Mayo Risk Score and MELD score will be calculated from baseline lab values. Subjects will complete the 24 week treatment course and undergo repeat MRE and laboratory testing. Laboratory testing and assessments for adverse events will be conducted at Weeks 2, 4, 12, 24, and 36. Details are given in the Time and Events Schedule.

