**Figure 1. Study Design Schematic**

Screening	Abatacept 125 mg SC				Off-Treatment FU	
Week	0	2	4	12	24	36

PROTOCOL TITLE: ABATACEPT FOR THE TREATMENT OF PRIMARY BILIARY CIRRHOSIS WITH AN INCOMPLETE BIOCHEMICAL RESPONSE TO URSODEOXYCHOLIC ACID

Time and Events Schedule for Protocol [IM101-457]

Procedures	Pre-Treatment Visit	Treatment Day 1	Treatment Week 2	Treatment Week 4	Treatment Week 12	Treatment Week 24	Post-Treatment Week 36 
Eligibility Assessments							
Informed Consent	X						
Inclusion/Exclusion	X						
Medical History							
Safety Assessments							
Physical Exam	X					X	
Vital signs	X	X	X	X	X	X	X
Signs and Symptoms		X	X	X	X	X	X
Adverse Events		X	X	X	X	X	X
ECG	X						
PPD	X						
HCV antibody	X						
HBs antigen	X						
HIV antibody	X						
UPT 	X	X		X	X	X	
Efficacy Assessments							
CMP	X	X	X	X	X	X	X
CBC	X	X	X	X	X	X	X
INR	X	X	X	X	X	X	X
CRP	X			X	X	X	X
AMA	X	X	X	X	X	X	X
IgG, IgM, IgA	X	X	X	X	X	X	X
ANA	X	X	X	X	X	X	X
Lipid Panel	X				X	X	X
MR Elastography	X					X	
PBC-40	X					X	
CD44+CD62L-	X				X	X	X
PK/IMG Samples 		X		X	X	X	X
Clinical Drug Supplies							
Abatacept 125 mg SC once weekly		X	X	X	X	X	

 Also to be performed for any subjects discontinuing the study with documentation for reason for discontinuation.

 Weeks 4, 12, and 24 should be drawn pre-dosing. The precise PK sampling times relative to the actual dosing time must be accurately recorded on the eCRF. The date and time of sample collection must be recorded so that compliance with the sampling schedule can be confirmed.

PROTOCOL TITLE: ABATACEPT FOR THE TREATMENT OF PRIMARY  
BILIARY CIRRHOsis WITH AN INCOMPLETE BIOCHEMICAL RESPONSE TO  
URSODEOXYCHOLIC ACID

From the ICF:

The clinical study will be done only at UC Davis. The name and address of this study center and the investigator for this study center are listed on page 1 of this document. Authorized members of the study staff will do all study procedures.

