Summary statistics for abatacept concentrations from Week 0 to Week 24 will be tabulated. Lack of immunogenicity is defined as the absence of a positive antibody response generated against abatacept administered subcutaneously. The incidence of a positive response will be summarized. The data will be analyzed to assess immunogenicity and its potential effect on pharmacokinetics and safety.

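### PK summary statistics leave out whole subjects for an undefined dose interruption, so troughs drawn before the interruption drop out of the table

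*Combined protocol and SAP*

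**What the plan says.** The Pharmacokinetic Analysis Population (section 14, Populations for Analyses) has two layers. The reporting layer is inclusive: every concentration is to be shown for any subject with one dose or more and one result or more. For summarising, "only subjects without dose interruption will be included in the summary statistics". The second layer acts on subjects. The available text gives no rule by sample or visit. It also does not say whether a late injection, a single missed injection, a temporary hold or permanent stopping counts as an interruption.

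The summary affected is a secondary endpoint, listed under Endpoint Definitions as "Trough concentrations of abatacept from week 0 to week 24". The Analyses section states: "Summary statistics for abatacept concentrations from Week 0 to Week 24 will be tabulated".

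On timing, section 12 says that "20 subjects with PBC who have had an incomplete biochemical response to UDCA will be assigned to treatment with weekly subcutaneous injections", and treatment lasts 24 weeks. Footnote 2 to the Time and Events Schedule adds: "Weeks 4, 12, and 24 should be drawn pre-dosing". It also says: "The precise PK sampling times relative to the actual dosing time must be accurately recorded on the eCRF".

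The other analysis sets carry no such exclusion. Efficacy and safety take everyone with at least one dose. Immunogenicity takes everyone with at least one dose and one result.

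**The concern.** Two things look wrong.

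First, the rule reaches back in time. A dose missed at Week 20 cannot change a concentration drawn at Week 4 or Week 12, yet both values leave the summary with the subject.

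Second, membership of the summary is decided by what happens after baseline. Section 16 requires study drug to stop when, in the investigator's opinion, an adverse event, laboratory abnormality or intercurrent illness makes continuing contrary to the subject's interest. If such stops or holds count as interruptions, the tabulated troughs describe subjects who tolerated and adhered to treatment. The stated objective is to characterize PK in patients with PBC.

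At stake are the precision of the trough summaries, in a trial of at most 20 subjects, and the population they describe.

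**Working it through.** **The plan's own figures.** The plan states no PK sample size, PK precision or expected interruption rate. Its only design figures concern response counts (Sample Size Determination). Both reproduce with the exact binomial at N = 20: P(3 or fewer | 0.05) = 0.984 against the stated >98%, and P(4 or more | 0.30) = 0.893 against the stated 89%. Neither enters this point.

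**Inputs from the documents.** N = 20; weekly dosing for 24 weeks; pre-dose samples at Weeks 4, 12 and 24. With dosing from Day 1, about 4, 12 and 24 doses precede these three troughs. The maximum is 20 × 3 = 60 troughs.

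**Assumptions.** Each weekly dose is missed independently with probability q, and any one miss is an interruption. The documents supply neither, so a range is shown.

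**Formulas.** Let s_k = (1 − q)^k for k = 4, 12, 24.

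- Subjects kept under the current rule: 20 × s24.
- Troughs kept under the current rule: 60 × s24.
- Troughs drawn before any missed dose: 20 × (s4 + s12 + s24).
- Troughs dropped although drawn before any miss: 20 × [(s4 − s24) + (s12 − s24)].

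| q | s4 | s12 | s24 | Subjects kept of 20 | Troughs kept of 60 | Troughs of 60 before any miss | Dropped though before any miss |
|---|---|---|---|---|---|---|---|
| 0.5% | 0.980 | 0.942 | 0.887 | 17.7 | 53.2 | 56.2 | 3.0 |
| 1% | 0.961 | 0.886 | 0.786 | 15.7 | 47.1 | 52.7 | 5.5 |
| 2% | 0.922 | 0.785 | 0.616 | 12.3 | 36.9 | 46.5 | 9.5 |
| 5% | 0.815 | 0.540 | 0.292 | 5.8 | 17.5 | 32.9 | 15.4 |

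The last column uses unrounded probabilities. At 2% it is 20 × [(0.9224 − 0.6158) + (0.7847 − 0.6158)] = 20 × 0.4755 = 9.5. Subtracting the rounded totals gives 5.6 at 1% and 9.6 at 2%, which is a rounding effect only.

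**Precision against a sample-level rule.** Take q = 2% and, for illustration, exclude a trough only if one of the 4 preceding doses was missed. Each visit then keeps 0.98^4 = 0.922 of its troughs (60 × 0.922 = 55.3 in all), against 0.98^24 = 0.616 under the current rule. With equal between-subject spread, the ratio of standard errors is √(0.922 / 0.616) = 1.22. So standard errors under the current rule are about 22% larger than under this alternative.

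**The case against.** The strongest defence is that the rule has a sensible purpose. The objective names abatacept 125 mg given weekly, and a summary of subjects who received it without a break describes exposure under that regimen. This stands as a reason to set aside troughs that follow a missed dose. It is not a reason to set aside a trough drawn before any dose was missed, since that value was obtained under full weekly dosing.

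A second objection is that nothing is lost, because every concentration is reported. This is right as far as it goes: a reader might infer that valid troughs are discarded, and they are not. They are missing only from the summary statistics. Reporting them elsewhere does not change what the tabulated summaries describe.

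Third, the figures rest on convenient assumptions. If the term means a sustained hold rather than a single missed injection, the table does not apply. If the same number of misses clusters in a few subjects, fewer subjects are excluded. If interruptions are rare, the effect is small, as the 0.5% row shows. All of this stands, and it is why the first step is to define the term.

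Fourth, PK is descriptive and secondary. It has no hypothesis test or decision rule, and the decision to pursue a randomized trial uses response counts only. That also stands, and it limits the severity.

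**Conclusion.** The point holds, at low severity. As written, the rule removes troughs that a later interruption could not have affected, and it conditions the PK summary on adherence and tolerance after baseline. Under the stated assumptions, with miss rates of 1% to 5% per dose, between 15.7 and 5.8 of 20 subjects would remain, and about 5.5 to 15.4 of 60 troughs would be dropped unnecessarily.

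Three stronger readings are tempting, and the documents do not support them:

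- *The reported exposure is biased upward.* Leaving out troughs after missed doses would tend to raise the mean. If high exposure led to adverse events and so to interruption, selection would work the other way. The documents give nothing from which direction or size can be derived.
- *Interrupted subjects are lost to the immunogenicity-PK or safety analyses.* The restriction is worded for the summary statistics. The plan for the linked analysis, "The data will be analyzed to assess immunogenicity and its potential effect on pharmacokinetics and safety", carries no such exclusion, and the safety and immunogenicity sets keep interrupted subjects. The analysis set for the PK link is simply not named.
- *Standard errors rise by 27% at a 2% miss rate.* That figure, √(1 / 0.616), compares with keeping all 20 subjects, which a sample-level rule would not do either. Against the illustrative 4-dose window the figure is 22%. If only troughs before the first miss were kept, there would be no gain at Week 24.

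**What to change.** Three changes to the Pharmacokinetic Analysis Population paragraph:

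1. Define dose interruption for analysis purposes, stating how late, missed, held and permanently stopped doses are classed.
2. Exclude individual troughs rather than subjects: leave a trough out of the summary only when dosing in a window before it, fixed before the analysis, was missed or late. The 4-dose window above is an illustration, and the study team should choose and justify its own.
3. Show beside it a summary of all dosed subjects with at least one concentration result.

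The eCRF must already hold sampling times relative to actual dosing, which supports a rule by sample. A window longer than one dose also needs the dates of the earlier doses in it, but the current rule needs dosing histories too.

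The cost is a short edit and one extra table. The drawback is that the number of subjects will differ between visits, so each visit's n must be shown. The sample size, primary endpoint and go/no-go rule do not change.
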